**Abbreviations List**

AE=Adverse event
BRT=Brake reaction time
CBD=Cannabidiol
CO-I=Co-investigator
DSST=Digital Symbol Substitution Test
IRB=Institutional Review Board
IT=Information Technology
PHI=Protected health information
PI=Principal Investigator
PVT=Psychomotor Vigilance Test
SRT=Simple Reaction Time test
SSS=Stanford Sleepiness Scale
THC= Delta-9-tetrahydrocannabinol
TMT=Trail Making Test
US=United States
VAMS=Visual Analog Mood Scale
WVU=West Virginia University

**Research Summary**

**Study Population** – Forty overall healthy adults will be recruited and randomized to receive either 300 mg of CBD (N=20) or placebo (N=20). The criteria for eligibility are as follows: 1) the participant must be currently enrolled as a WVU student, 2) be 18-30 years of age at time of study, 3) have a current drivers' license issued from any state in the United States, 4) has driven at least once in the past 30 days 5) is able to speak and read English, 6) is willing to be randomized and comply with study requirements including a urine drug test on the day they consent to participate in the experiment and complete a test drive to ensure the absence of simulation sickness, 7) not currently taking any daily prescription medications other than birth control, 8) have not been diagnosed with any serious chronic disease by a licensed healthcare provider (including but not limited to Alzheimer's and related dementias, Parkinson's disease or other neurodegenerative disorder, major depressive or anxiety disorder, schizophrenia or other serious mental illness, arrhythmias, cataracts, glaucoma, chronic obstructive pulmonary disease, diabetes, epilepsy, sleep apnea, and fibromyalgia), and 9) has an individual able to drive them home after testing or is willing to be driven home by study staff after testing completion.

Participants will be excluded if they 1) currently smoke or use tobacco products, 2) have used illegal drugs (including cocaine/crack, heroin, methamphetamine, 3,4-methylenedioxy-methamphetamine, inhalants, phencyclidine, lysergic acid, mushrooms, or marijuana) in the past 30 days, 3) has consumed CBD in the past 7 days, or 4) is currently pregnant or lactating. The health conditions and substances noted above have all been associated with changes in driving ability or performance. Also, limiting participants to those who are currently not using illegal drugs, tobacco products, and prescription medications may help minimize bias potentially caused by drug interactions with CBD or known impediments to driving performance from the medications themselves. Because the safety of CBD on fetuses or neonates is unknown, individuals who are pregnant or lactating are excluded for safety reasons.

**Study Design** – This is a randomized, parallel-group, double-blind, exploratory two-arm trial to assess the effects of CBD on driving ability along with changes in psychological status (e.g., sedation) and cognitive function. Forty healthy West Virginia University (WVU) students will be recruited for this study. Email notifications about the study will be sent to the student body and flyers will be posted on boards throughout campus; this type of recruitment has been successful in our other studies. Interested students can contact study personnel. Study personnel will tell them about the study and pre-screen participants using a standardized checklist. If students are eligible and still want to participate, they will be asked to meet at the research office. After eligibility is reassessed and consent is obtained, the individual will be allocated and randomized to receive: (1) 300 mg of pure CBD oil or (N=20) (2) placebo matched in appearance and taste (N=20). After consuming the study drug, each individual will participate in a 25–35-minute driving simulation (which includes a practice drive and brake reaction test (BRT)) and have their driving performance measured. To assess changes in mental status (i.e., sedation and drowsiness) and drug impairment-related cognitive

function, the VAMS, SSS, DSST, PVT, SRT, and TMT will also be administered to participants at baseline (prior to study drug consumption) and following completion of the driving simulation test. The primary outcome of this study will be driving performance, quantified using measures strongly associated with collision risk including number of lane departures, standard deviation of lateral position (i.e., weaving), brake reaction time, and collision occurrence. Secondary outcomes will be pre-post changes in well-validated measures of mental sedation (VAMS, SSS) and cognitive function (DSST, TMT, PVT, SRT). We will also collect baseline demographic, health, and driving history data along with data at the end of the survey to assess participant satisfaction and tests of blinding. The entire protocol for each participant will be completed in one day and should take 4-4.5 hours to complete. We chose a parallel design as opposed to a cross-over design to minimize participant burden (i.e., to avoid 2 testing sessions) and facilitate retention. As CBD is a legal nutraceutical that can be obtained over the counter, and it typically is well-tolerated, this study is minimal risk. All data will be deidentified and stored on a secure server that is compliant with WVU Information Technology (IT) Department. An overview of the protocol is below.

**Study Duration** – 24 months

## Section II: Design

**Background & Significance**

**BACKGROUND.** Drug-impaired driving has outpaced alcohol-impaired driving in the United States (US) partly due to the passage of state medical and recreational marijuana use laws and the national opioid epidemic. Delta-9-tetrahydrocannabinol (THC), the psychoactive component of marijuana (*Cannabis sativa*), is consistently the most prevalent drug identified among drivers nationally and its detection has increased nearly 50% since 2007. THC is known to impair drivers' psychomotor function, divided attention, lane tracking, and cognitive function, which can increase their risk of motor vehicle collision. While knowledge of the pharmacodynamic and pharmacokinetic properties of marijuana are expanding, virtually nothing is known regarding the effects of cannabidiol (CBD), the non-psychoactive component of marijuana, and its relationship with driver performance, despite rapidly increasing use and health claims.

Although little is known about CBD's effects, it is a legal substance in the US and is currently being added to a myriad of foods, beverages, tobacco products, and dietary supplements in oil or tincture form. CBD is immensely popular and sales are projected to hit \$23 billion per year by 2025. A survey of US CBD consumers (N=2,409) revealed that many individuals purchase the product for general wellness or recreation (38%), but most use CBD to treat a medical condition (62%), such as pain, anxiety, depression, or insomnia. Whether CBD actually helps these maladies is unclear; peer-reviewed placebo-controlled studies of CBD have only been conducted in small, unique clinical populations suffering from conditions such as post-traumatic stress, addiction, anxiety, multiple sclerosis, epilepsy, psychosis, movement disorders, or insomnia. While most studies involving clinical populations show that CBD is well-tolerated in high doses, it is not without its side effects; patients often claim to experience drowsiness and sedation. In fact, the Food and Drug Administration package insert for Epidiolex, which is prescription CBD oil for Lennox-Gastaut and Dravet syndromes in children, contains a warning about sedation and potential driver impairment. However, the effects of CBD in healthy adult populations is severely lacking, especially with regard to effects on driving.

To our knowledge, only 16 placebo-controlled peer-reviewed studies of CBD have been conducted to date in healthy volunteers; most of these studies have been conducted using males and virtually all have involved South American or European populations. The sample sizes are small with 79% of these studies having fewer than 16 people (range 5-57 participants); all these studies have suggested that CBD is sedating and anxiolytic but were not statistically significantly different from the effects of placebo, which is likely driven by the very small sample sizes. Surveys indicate that females appear to use CBD more than males, but the known effects of CBD are virtually unstudied in healthy females. Thus, it appears that CBD is likely sedating, but it has not been formally assessed in a placebo-controlled trial in a healthy US population consisting of both sexes. Additionally, to date, no peer-reviewed studies have investigated whether CBD alone affects the driving ability of healthy adults.

Thus, the **objectives** of this application are to investigate the effects of CBD on driving performance, psychological status (i.e., mood, drowsiness, sedation), and cognitive function in healthy adults aged 18-30 years. Driving performance will be assessed using a driving simulator, which directly correlates with actual driving ability, while cognitive function and psychological status will be assessed using a battery of well-validated instruments widely used in the evaluation of drug impairment. Given that CBD products are growing exponentially in popularity among all age groups, and their effects in a healthy population are understudied, the **positive impact** of this study is the collection of essential preliminary data regarding the potential adverse effects of CBD, which may unknowingly put drivers and other road users at increased risk of motor vehicle collision and subsequent morbidity and mortality.

**SIGNIFICANCE.** West Virginia has a traffic fatality rate that is 70% greater than the national rate. While the exact reason for this disparity is unclear, previous studies have suggested that drug impaired driving may be partly responsible. Not only is the traffic fatality rate elevated in WV, but our preliminary studies indicate that CBD consumption is high as well. Among WVU students, our preliminary study found that 60% of drivers surveyed had consumed CBD (see section C.5.4.1). This demonstrates the high usage in the population and the need to determine if CBD is safe for drivers to consume not only nationally, but also in WV, which already suffers from such a disparate traffic fatality rate. These findings could facilitate public health intervention, driver education, and/or legislative initiatives to protect this high-risk population of drivers.

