## Objectives

The **objective/purpose** of this study is to investigate the effects of CBD on driving performance, psychological status (i.e., mood, sedation, drowsiness), and cognitive function in healthy adults aged 18-30 years. This is because CBD is widely sold and consumed and there is some evidence that it may be sedating; however, this has never been evaluated in healthy adults. The **primary outcome** of this study will be driving performance, quantified using measures strongly associated with collision risk, including number of lane departures, standard deviation of lateral position (i.e., weaving), brake reaction time, and collision occurrence. Driving performance will be assessed using a driving simulator. **Secondary outcomes** will be changes in well-validated measures of mental sedation and cognitive function which includes performance on the VAMS, SSS, TMT, DSST, PVT, SRT. The VAMS and SSS are Likert-type scales which assess mental and physical sedation and sleepiness, respectively, at that moment and time. VAMS consists of 16 questions, while SSS only consists of 1. These measures can be summed with higher scores equating to more sedation. The SSS will be summed with greater perceived sleepiness receiving a larger score, similar to the VAMS. The DSST measures psychomotor speed, attention and working memory by requiring participants to translate numbers into symbols; the test is scored by the degree of completion and accuracy over a timed 90 second period. The TMT measures executive function and consists of two parts; the first part requires participants to connect numbers in ascending order, while the second part requires individuals to connect numbers and letters in sequence. The test is scored by the time it takes to accurately complete each test. Increases in time correlate with greater impairment. PVT and SRT are tests given on a computer tablet. They both measure participants reactions to stimuli.

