## Study Design & Methodology

This is a randomized, parallel-group, double-blind, exploratory two-arm trial to assess the effects of CBD on driving ability along with changes in psychological status (e.g., sedation) and cognitive function. Thus, the data will be collected prospectively. The methodology of the study is below.

**Study Design and Protocol Overview.** We propose a randomized, parallel-group, double-blind, exploratory two-arm trial to assess the effects of CBD on driving ability along with changes in psychological status (i.e., mood, drowsiness, sedation) and cognitive function. Forty healthy West Virginia University (WVU) students will be allocated and randomized to receive: (1) 300 mg of pure CBD oil or (N=20) (2) placebo matched in appearance and taste (N=20). After consuming the study drug, each individual will participate in a 25–35-minute driving simulation, which includes a practice drive and brake reaction test, and their driving performance measured. To assess changes in psychological status (i.e., mood, drowsiness, sedation) and drug impairment-related cognitive function, the VAMS, SSS, DSST, TMT, PVT, SRT will also be administered to participants at baseline (prior to study drug consumption) and following completion of the driving simulation test. The primary outcome of this study will be driving performance, quantified using measures strongly associated with collision risk including number of lane departures, standard deviation of lateral position (i.e. weaving), reaction time, and collision occurrence. Secondary outcomes will be pre-post changes in well-validated measures of mood, drowsiness, mental sedation (VAMS, SSS) and cognitive function (DSST, TMT, PVT, SRT). We will also collect baseline demographic, health (including body mass index), and driving history data, including driving habits, along with data at the end of the survey to assess participant satisfaction and tests of

blinding. The entire protocol will be completed in one day and should take 4-4.5 hours to complete for each participant. We chose a parallel RCT design as opposed to a cross-over RCT to minimize participant burden, while still being able to study both within individual (i.e., test battery results) and between group effects (i.e., simulator and test battery performance).

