These tests have all been deemed valid and reliable instruments and have been described in detail elsewhere. The tests will be administered by trained study personnel via a computer tablet and/or paper and pencil; personnel will then transfer the collected data to a secure, electronic database. Participants will also be given a standardized breakfast after baseline assessment.

**Allocation, Randomization and Blinding.** Participants will be randomized immediately after baseline assessments are completed to the CBD (N=20) or placebo group (N=20) using a sex-stratified 1:1 random block design to ensure equal distribution among treatment groups and sex. The participant and the PI will be unaware of group assignment (i.e. double-blind). [name], who will not have contact with participants, will generate a randomized assignment master list and provide sequentially numbered envelopes containing group assignment to the team member that helps consent participants. This team member will assign the unique number from the next envelope in sequence as the participant's study identification number and will record the participant's information in a secure, electronic master database.

**Intervention.** Protocol A consists of a 300 mg dosage of CBD oil which will be consumed orally. This dosage was chosen as it has been used in other studies consisting of both healthy and clinical populations and is well-tolerated with no major adverse events. CBD will be obtained from Zatural, a CBD manufacturer from Eden, Idaho. The CBD oil will be tested by Botanacor Laboratories (Denver, CO) for microbials, potency, heavy metals, trace THC, pesticides, and residual solvents to ensure purity, label accuracy, and safety; copies of laboratory reports will be maintained on premise. Protocol B is a placebo matched on appearance to the treatment (i.e., avocado oil potentially colored with food coloring). Both the CBD oil and placebo will be matched on taste (i.e., peppermint-flavored oil) prior to dispensing to each participant. After consumption of the respective protocol drug, the participant will be given a standardized meal and will then wait for 120 minutes to allow for digestion and for CBD to begin taking effect; this time frame was chosen based on the pharmacodynamics of CBD along with the consideration of participant burden (max absorption 2-5 hours). Next,

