## Statistical Analysis Plan

All collected data will be entered by study staff into the secure, de-identified database and maintained in accordance with WVU IRB. All analyses will be performed in SAS (Cary, NC). The primary outcome of this study will be driving performance, including number of lane departures, standard deviation of lateral position (i.e., weaving), mean brake reaction time, and number of collisions (Aim 1). Secondary outcomes will be pre-post changes in well-validated measures of mental sedation (SSS, VAMS) and cognitive function (DSST, TMT, PVT, SRT) (Aim 2). The variables that will be collected and their source are summarized in Table 2. Missing data will be multiply imputed to allow inclusion of all participants regardless of compliance. We will perform both an intent-to-treat analysis based on initial assignment and a protocol

analysis, excluding those who fail to complete the study. Both between and within-group analyses will be conducted. Demographic characteristics will be compared between groups via descriptive statistics to ensure proper randomization; we will also investigate tests of blinding by comparing accuracy of group assignment (perceived group assignment will be asked on end of study survey). For between group effects, the data will be compared using Student's T-tests and/or ANOVA for continuous variables if the data are normally distributed; if non-normally distributed a Mann-Whitney test may be utilized. For within group effects, the data will be compared using paired Student's T-tests (for continuous paired observations which are normally distributed) or Wilcoxon signed-rank test (for continuous paired observations which are not normally distributed). We will perform a correlation using Pearson's R test between the variables collected for Aims 1 and 2, both between and within groups, to assess whether driving performance is correlated with psychological or cognitive testing measures. Data will also be analyzed via sex.

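### The plan tests the driving measures only for a difference, with no effect estimate, confidence interval or rule for a null result, so with 20 students per arm a non-significant finding could be over-read as reassurance about CBD and driving

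*Combined protocol and SAP*

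**What the plan says.** The significance paragraph of Background & Significance justifies the trial by "the need to determine if CBD is safe for drivers to consume not only nationally, but also in WV" and continues: "These findings could facilitate public health intervention, driver education, and/or legislative initiatives to protect this high-risk population of drivers".

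The formal statements are more modest. Under Objectives, the purpose "of this study is to investigate the effects of CBD on driving performance, psychological status" and cognitive function. Study Design & Methodology describes a "randomized, parallel-group, double-blind, exploratory two-arm trial to assess the effects of CBD on driving ability". The Background section says that the positive impact "of this study is the collection of essential preliminary data regarding the potential adverse effects of CBD".

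On analysis, the Statistical Analysis Plan says: "For between group effects, the data will be compared using Student's T-tests and/or ANOVA for continuous variables if the data are normally distributed". A Mann-Whitney test is the fallback. Paired tests, Pearson correlations and an analysis by sex complete the list. Neither there nor in the data analysis paragraphs of Study Design & Methodology is there a between-group effect estimate, a confidence interval, a smallest important impairment, a margin, or a rule for reporting a null result.

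The Sample Size paragraph is based on mean reaction time. It claims 80% power with 26 students in total for an effect size of 0.7, described as large, in a two-sided two-sample t-test at 0.05. It concludes that 40 is ample.

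Of earlier placebo-controlled CBD studies in healthy volunteers, with 5 to 57 participants, the Background section says that the effects "were not statistically significantly different from the effects of placebo, which is likely driven by the very small sample sizes".

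**The concern.** A test of no difference can give evidence of impairment. When it is not significant, it cannot by itself separate an effect too small to matter from data too sparse to tell. The protocol raises a safety question, foresees use in education and legislation, and assures the reader that the sample is ample. It provides p-values and nothing that shows how large an impairment remains possible.

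The protocol knows the problem: it attributes earlier non-significant results to small samples. A trial of 40 lies inside the size range it gives for those studies, yet the analysis plan contains no safeguard. At stake is false reassurance to drivers from a result that is only inconclusive.

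**Working it through.** **Inputs.** 20 per arm (40 students, 1:1), alpha 0.05 two-sided, effect size 0.7 SD, 80% power, equal-variance t-test: all from the protocol. The documents give no SD and no smallest important impairment, so everything below is in SD units. The 0.5 SD and smaller effects are illustrative assumptions.

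**The plan's own figure.** With n per arm and standardized difference d, the t statistic has 2n − 2 degrees of freedom and noncentrality d / √(2/n).
- 26 in total (13 per arm), d = 0.7: power is 40%, not 80%.
- 80% power at d = 0.7 needs 34 per arm, 68 in total.
- The number 26 is recovered only as a per-arm size for a one-sided test (power 80.1%), which would be 52 in total.

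The assurance about N = 40 therefore does not follow, even for detecting a difference.

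**Power at 20 per arm.** √(2/20) = 0.316.
- d = 0.7: noncentrality 0.7/0.316 = 2.21; power 58%, so a true effect of this size is missed in 42% of trials.
- d = 0.5: noncentrality 0.5/0.316 = 1.58; power 34%, missed in 66%.
- Effect detectable with 80% power: 0.91 SD.

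**Precision at 20 per arm.** Half-width of the 95% interval = t(0.975, 38) × √(2/20) = 2.024 × 0.316 = 0.64 SD, taking the sample SD equal to the true SD.
- Observed difference zero: upper limit 0.64 SD, just under 0.7.
- Largest non-significant difference, about 0.64 SD worse: upper limit 2 × 0.64 = 1.28 SD.
- To exclude 0.7 SD, the observed difference must be at most 0.70 − 0.64 = 0.06 SD.
- To exclude 0.5 SD, it must be at most 0.50 − 0.64 = −0.14 SD, so the CBD arm must look better than placebo.

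**How often a null result would reassure.** If the true effect is zero, the chance that the upper limit falls below a worsening m equals the power of a one-sided 0.025 test at d = m: 58% for 0.7 SD and 34% for 0.5 SD. Among non-significant results only, from 200,000 simulated trials per row:

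| True worsening (SD) | Non-significant | Of these, upper limit below 0.7 SD |
|---|---|---|
| 0 | 95% | 58% |
| 0.2 | 91% | 37% |
| 0.35 | 81% | 23% |
| 0.5 | 66% | 14% |

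**Size needed to exclude a worsening.** With true effect zero, one-sided 0.025, 80% power and the normal approximation, n per arm = 2 × (1.960 + 0.842)² / m². For m = 0.7: 2 × 7.85 / 0.49 = 32.04, so 33 per arm, 66 in total. For m = 0.5: 2 × 7.85 / 0.25 = 62.8, so 63 per arm, 126 in total.

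**The case against.** The strongest reply is that this is not a safety trial. The sentence about safety describes a background need. The objective is to investigate effects, the design is labelled exploratory, the output is preliminary data on adverse effects, and the Background section expects CBD to be sedating. A difference test suits that aim. The legislative sentence speaks of protecting drivers, which would most naturally follow from a detected impairment. All of this stands and limits the point to reporting. It does not remove it: an exploratory trial is where estimates with intervals are most informative, and the plan has none.

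Three stronger readings are tempting, and the documents do not support them.

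- *A reader might infer that p > 0.05 will be announced as safety.* No section says so, and the comment on earlier small studies points the other way. What can be said is that the plan leaves that reading open.
- *A reader might infer that a non-significant result can never exclude a large impairment.* It sometimes does: an observed difference of zero or in favour of CBD gives an upper limit below 0.7 SD.
- *A reader might infer that the drive takes place 2.0 to 2.6 hours after dosing, at the very start of the stated 2-5 hours to maximum absorption.* The Intervention paragraph places a standardized meal of unstated length after dosing; participants then "wait for 120 minutes to allow for digestion and for CBD to begin taking effect". The drive starts later than 2.0 hours by an unknown amount, so neither that window nor a share of participants past their peak can be derived.

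Lane departures and collisions are counts, so the SD-scale figures do not carry over to them directly.

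**Conclusion.** The point holds as one of analysis and reporting. The protocol raises a safety question and answers it for the driving measures with difference tests alone, supported by a sample-size assurance that does not reproduce. With 20 per arm, non-significance by itself often does not exclude the plan's own large effect: the interval is ±0.64 SD, power is 58% at 0.7 SD and 34% at 0.5 SD, and even with no true effect the upper limit clears 0.7 SD in only about 58% of trials.

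The figures assume approximately normal data, equal variances, no dropout and one endpoint tested at 0.05. They apply to brake reaction time and lateral position.

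**What to change.** In the Statistical Analysis Plan:

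1. Make the CBD-versus-placebo estimate with 95% confidence interval the reported result for each driving measure: a mean difference (CBD minus placebo) for brake reaction time and lateral position, and a count-appropriate estimate such as a rate ratio for lane departures and collisions. P-values may accompany these.
2. State that a non-significant result is inconclusive, not evidence of safety, unless the upper limit excludes a worsening stated in advance. The plan's 0.7 SD is the only reference size in the documents. It comes from the power calculation and is not a justified margin; a smaller one would need its own justification.
3. Record for each participant the time from dosing to the drive, and limit the conclusion to one 300 mg dose at the times actually tested.
4. Withdraw or correct the statement that 40 is ample.

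The cost is wording and one recorded time per participant, with no added recruitment. The downside is that null results will often have to be reported as inconclusive.
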